9.2.3 Reporting Procedures for Serious Adverse Events

Serious adverse events (SAEs) which occur as the result of an incident during, or within two hours of completing, the exercise sessions or follow-on physical activities, and are considered related to the study, will be reported in a pre-defined and time-critical process. The site PI or delegated team member must assess causality of any suspected SAEs and report them to the BOOST-IS Team within 24 hours of becoming aware of the event, using the Serious Adverse Event Form for non-CTIMPs. Completed forms will be scanned and emailed to the BOOST-IS Team, who will assess causality and expectedness, and ensure that all SAEs are followed up to resolution. Any unexpected SAE which is deemed related to the study interventions will be reported to the REC that gave a favourable opinion of the study by the BOOST-IS Team within 15 working days of the Chief Investigator becoming aware of the event, using the Health Research Authority (HRA) report of serious adverse event form (see HRA website).

9.3 Research Ethics Committee (REC) and other Regulatory review & reports

Before the start of the study, a favourable opinion will be sought from the UK Health Departments Research Ethics Service (NHS REC and HRA assessment) for the study protocol, informed consent forms and other relevant documents. We will ensure that:

- Substantial amendments requiring review by NHS REC will not be implemented until
 that review is in place and other mechanisms are in place to implement at site.
- All correspondence with the REC will be retained.
- The Chief Investigator will notify the REC of the end of the study.
- The CI shall submit, on request, an Annual Progress report to the REC Committee, host organisation and Sponsor.
- If the study is ended prematurely, the Chief Investigator will notify the REC, including the reasons for the premature termination.
- Within one year after the end of the study, the Chief Investigator will submit a final report with the results, including any publications/abstracts, to the REC.

9.3.1 Regulatory Review & Compliance

Before any site can enrol patients into the study, we will ensure that appropriate approvals from participating organisations are in place. For any amendment to the study, we will, in agreement with the sponsor, submit information to the appropriate body in order for them to issue approval for the amendment. We will work with sites (R&D departments at NHS sites as well as the study delivery team) so they can put the necessary arrangements in place to implement the amendment to confirm their support for the study as amended.

9.3.2 Amendments

The Investigator will submit and, where necessary, obtain approval from the Research Ethics Committee and Sponsor for all substantial amendments to the original approved documents. It is the sponsor's responsibility to decide whether an amendment is substantial or non-substantial for the purposes of submission to the REC.

9.4 Patient & Public Involvement

PPI has been and will continue to be central to the optimisation and implementation of the BOOST programme. We have established a diverse community of practice (COP) consisting of physiotherapists from the original BOOST trial, patients who received the BOOST programme in the original trial, physiotherapy managers, clinical commissioners, and clinicians with expertise in symptomatic lumbar spinal stenosis (LSS). This COP has iteratively co-produced the optimised elements of the BOOST programme with the study team. We will continue to utilise this COP to help champion the BOOST programme and establish an impactful implementation strategy. Furthermore, all patient facing materials have been reviewed by patients in this COP.

9.5 Protocol compliance

Accidental protocol deviations can happen at any time. They must be adequately documented on the relevant forms and reported to the Chief Investigator and Sponsor immediately. Deviations from the protocol which are found to frequently recur are not acceptable, will require immediate action and could potentially be classified as a serious breach.

9.6 Data protection and participant confidentiality

9.6.1 Participant confidentiality

The study staff will ensure that participants' anonymity is maintained. Participants will be identified by a unique personal identification (ID) code on all outcome measures and in any electronic database holding study data. Participants will not be named on the qualitative interview transcripts and care will be taken to remove any identifying information given in interviews.

All documents will be stored securely at the University of Exeter study offices and only accessible by study staff and authorised personnel. The study will comply with the Data Protection Act and any personal details (e.g. addresses for posting follow-up questionnaires) held by the study team will be stored separately from any participant study data. All study data will only be accessed by authorised personnel. The consent form includes consent for this data to be held. Data linking participants with their unique ID will be stored in separate locations using encrypted digital files with password protected folders.

For the activity informatics team at the University of Exeter to send the wrist worn accelerometer to patient participants at baseline, the BOOST study team will send them a link to a file on OneDrive that contains the participants name and postal address. The activity informatics team will write the details on the envelopes for posting and will then email the BOOST study team to confirm that the data has been received. The link to the OneDrive file will then be removed. We will repeat this process to send the accelerometers to participants at the 6-month follow-up time point.

9.6.2 Data processing

The Chief Investigator (CI) will be responsible for the management of the research data throughout the life of the project. Local Principal Investigators at each institution will be responsible for research data management at that institution. The CI will have overall responsibility for data management. Documentation from the cohort studies will be retained for 5 years after completion of cohort-related activities. Collaborating sites are delegated the responsibility of archiving local essential documents (including the Investigator Site File) in an appropriate secure environment. The study team will archive all documents according to University of Exeter policy. A master copy of the data will be stored. No analysis will be run on this copy so if the working copy gets corrupted, lost or becomes unusable we will be able to create an identical working copy. Only fully anonymised data will be shared at the end of the

project.

Patient participants

We will ask the therapist delivering the BOOST programme to scan and email the study enrolment form (containing the participants contact details), consent form and the baseline/follow-up questionnaire (PROM and 6MWT) to the study team's secure NHS email. These will be stored in the University's Research Data Storage (RDS) platform, a large object store that replicates across three sites allowing for high resilience and reliability. Data will be inputted into Excel files stored on the University's RDS platform. We will double check ten percent of data for errors. If a participant does not attend their 6-month follow-up appointment and is therefore unable to complete the outcome measures, the study team will post these to the participant along with a self-addressed, pre-paid envelope. On return, these will be scanned and stored on the same secured network drive, with the paper copies securely destroyed. Files will only be accessed by designated members of the study team.

Data from the original BOOST RCT that will be used to generate the synthetic controls will also be stored on the University's RDS secure platform.

Data from the wrist worn accelerometer is stored locally on the device. On receipt of the devices return, the activity informatics team at the University of Exeter will transfer data from the device to their research grade, secure cloud server. Once analysed, the activity informatics team will transfer the pseudo-anonymised output files to the BOOST study team using the University's secure OneDrive. These files will then be downloaded into the University's RDS storage and merged with the remaining study data by the study's statistician. The anonymised monitoring log that participants return with their wrist worn accelerometer will be used to facilitate data analysis by the activity informatics team and will be stored securely in locked filing cabinets at the University of Exeter.

Therapist participants

Data from the BOOST MOOC evaluation will be collected using JISC online surveys. Each participant will have a unique ID that links their anonymised survey responses. Data will be downloaded from JISC and stored securely in the University's RDS platform. Files will only be accessed by designated members of the study team.

Therapist interviews will be conducted on MS Teams and will be audio-video recorded and automatically transcribed. These files will be automatically downloaded to the University of Exeter's cloud-based storage solution (OneDrive) and will be manually moved onto the University's RDS platform for secure storage.

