6.1 Data Collection

Patient participants

A reduced set of outcome measures from the original BOOST RCT will be used to evaluate the effect of implementation on patient outcomes (Table 1). Participants will complete a baseline questionnaire consisting of demographic information (age, sex, ethnicity, household income, education attainment, place of residence, marital status, and employment status), medication use, co-morbidities and patient reported outcomes (Oswestry Disability Index (ODI), Health-related quality of life (EQ-5D-5L), 4-items from the CSEP-PATH: Physical activity and sedentary behaviour questionnaire (PASB-Q), and a single item question on how troublesome their symptoms have been). The therapist will also complete the 6-minute walk test at baseline and record this in the participant's baseline questionnaire. Participants will attend an additional clinic appointment at 6 months to complete a follow-up questionnaire consisting of patient reported outcomes (ODI, EQ-5D-5L, 4 items from the PASB-Q, a single item question on how troublesome their symptoms have been, and an 8-item satisfaction questionnaire). The therapist will repeat the 6-minute walk test and record this in the participant's follow-up questionnaire.

In addition, we will collect an objective measure of activity over time, utilising a CE marked wrist worn accelerometer provided by the Activity Informatics team at the University of Exeter. The research device is a black 'watch' and does not present any data to participants. Participants will wear the device for 16 days to capture two weekends at baseline and at the 6-month follow-up timepoint. Participants will receive the wearable via post, along with instructions on how to wear it and how to return it in the pre-paid envelope provided. While using the device, participants will complete an activity log to record i) the date they put the device on, ii) the date they removed the device, iii) details of why they have removed the device for any period during the 16 days and for how long, and iv) to facilitate accuracy of the data analysis, the time they went to sleep and woke up. Assessment time points are outlined in Table 2.

Table 2: Patient participant outcomes and assessment time points

	Timepoint					
Stages 1 and 2	Baseline	6-months follow-up				
Informed consent	Х					
Demographics	х					
Medications and co-morbidities	х					
ODI	х	x				
EQ-5D-5L	X	х				
PASB-Q	X	х				
6-minute walk test	X	х				

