7.1.4 Exclusion Criteria

Not meeting the inclusion criteria.

7.2 Recruitment Stage 1

Site recruitment

All physiotherapists who took part in the BOOST RCT will be contacted via email to inform them about an opportunity to participate in stage 1 and/or stage 2 of the BOOST programme optimisation and implementation. If this does not result in 4 NHS sites for stage 1, we will seek additional new sites (that did not participate in the BOOST RCT) based on our clinical networks. For 3 of the NHS sites, the BOOST programme will be delivered within the NHS as it was in the original RCT. For the forth NHS site, the BOOST programme will be delivered in the community with a local provider who has a good existing relationship with the NHS Trust.

We will conduct semi-structured interviews with all the therapists (n=4) delivering the optimised BOOST programme to understand the impact of the changes made to the programme.

Patient participant recruitment

Potentially eligible patients will be identified either from (i) physiotherapy waiting lists or (ii) from an initial consultation with a physiotherapist. Where identified from a waiting list, the patient will be sent the patient information sheet via post or email, depending on their preference, with a follow up phone call to ascertain if the patient would be interested in taking part. Where identified in an initial consultation with a physiotherapist, the physiotherapist will screen the patient for eligibility and provide the patient information sheet to the patient. Depending on the set up at each site, either a research physiotherapist in the NHS physiotherapy outpatient department, or the physiotherapist who conducted the initial consultation with the patient, will consent patients for the study, complete the study enrolment form (containing the participants contact details) and carry out the baseline assessment. For the site where BOOST will be delivered in the community, participants will be booked an individual appointment with the community provider to complete their baseline outcome measures and receive the first individual BOOST session. While the programme is running in the community, the referring physiotherapist will hold a consulting role, supporting the community provider as and when needed.

Stage 2

Therapist participant recruitment

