8.2 Data Analysis

Outcome hierarchy

Primary outcomes: ODI walking item and the 6-minute walk-test

Secondary outcomes listed in order of priority: ODI standing item, ODI pain item, ODI overall, followed by all remaining outcome measures.

Stage 1

We will use a synthetic control method to evaluate the probability that the optimisation has improved the intervention (20). Synthetic controls are a method of using historical control data, and contemporary data on the natural history of a condition, to form the counterfactual element needed to draw inferences on the improvement cycles. The counterfactual state is one which estimates what would happen if the improvements were not made, or no intervention was made. The rich data set from the BOOST trial will allow us to create a counterfactual that accounts for context, and to draw a comparison with the BOOST group intervention as well as a comparison to the control arm of the BOOST trial (best practice advice).

Two different analytical approaches will be used to enable synthetic control comparisons. First, propensity score methods will be employed to balance measured covariates at baseline between the group receiving the optimised programme and the control arm of the BOOST trial (21). We will consider a broad list of demographic and baseline clinical characteristics as covariates. The effectiveness of the optimised intervention will be estimated in generalised linear mixed models for the study outcome measures with inverse probability of treatment weighting (IPTW) on the propensity score (PS). Previous studies have shown that IPTW can produce valid estimates of treatment effects in small samples if relevant confounders are included in the PS model, but sensitivity analyses will be conducted to explore the impact of model specification and missing data (22). Random effects will be included to account for any heterogeneity in response due to the recruitment centre. As a second approach, Bayesian hierarchical linear models will be used to compare the optimised intervention to each arm of the BOOST trial, with commensurate and power priors to determine the degree of borrowing of information from the historical trial data. Models will be adjusted for key baseline characteristics to account for measured confounders (23). We will guard against baseline differences generating confounded effect estimates by recruiting in a similar way to the original trial and ensuring a representative population.

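### The delivering therapist handles patients' 6-month questionnaires and may run the walk test; no independent assessor is named, and baseline adjustment cannot correct any resulting bias

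*Protocol*

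**What the plan says.** Section 8.2 sets the hierarchy: "Primary outcomes: ODI walking item and the 6-minute walk-test". The first is a self-report item. The second is a performance test that depends on effort and encouragement.

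Section 6.1 describes the 6-month visit: "Participants will attend an additional clinic appointment at 6 months to complete a follow-up questionnaire consisting of patient reported outcomes". These include the ODI, and the same questionnaire carries "an 8-item satisfaction questionnaire". Of the walk test it says: "The therapist will repeat the 6-minute walk test and record this in the" follow-up questionnaire, so the distance and the patient's own answers sit in one document.

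Section 9.6.2 says who forwards it. "We will ask the therapist delivering the BOOST programme to scan and email the study enrolment form", along with the "consent form and the baseline/follow-up questionnaire (PROM and 6MWT) to the study team's secure NHS email". The one exception is a patient who misses the visit: the study team posts the forms with a pre-paid return envelope.

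For baseline, section 7.2 lets the assessment at NHS sites be done by "either a research physiotherapist in the NHS physiotherapy outpatient department, or the physiotherapist who conducted the initial consultation with the patient". At the community site, the provider who delivers the programme takes the baseline measures. No section gives a matching rule for 6 months.

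**The concern.** A patient who hands a questionnaire to the person who treated them may answer more kindly than one who returns it to a third party. A therapist who delivered the programme may, without intending to, encourage more in the follow-up walk test. Either would move a primary outcome in favour of the optimised programme.

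In a randomised comparison with the same procedure in both arms, much of this would cancel. Here the comparator is data from an earlier trial, and whether it cancels depends on how that trial collected its outcomes. The decisions at stake are whether the optimised programme replaces the original one after Stage 1, and whether the online course is launched widely after Stage 2.

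**Working it through.** The protocol gives no figure to reproduce on this point. The check is a reading of the sections side by side, followed by a short illustration.

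**Who touches the 6-month data**

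| Step | Protocol | Person named |
|---|---|---|
| ODI and satisfaction items completed | 6.1 | Patient, at a clinic visit |
| Walk test run and written into the same form | 6.1 | The therapist, not further specified |
| Form scanned and emailed | 9.6.2 | The therapist delivering BOOST |
| Form returned after a missed visit | 9.6.2 | Patient, by post to the study team |
| Baseline assessment, NHS sites | 7.2 | Research physiotherapist or consulting physiotherapist |
| Baseline assessment, community site | 7.2 | Community provider |

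Three things follow. The delivering therapist handles the completed self-report form and is able to see it. The 6-month walk-test assessor is not fixed, so it may be the deliverer and may differ from the baseline assessor. Patients who attend and patients who do not attend answer under different conditions of confidentiality.

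**What the analysis can correct**

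In section 8.2, propensity weighting balances covariates measured at baseline, and the Bayesian models adjust for key baseline characteristics. The stated safeguard of recruiting much as the original trial did also concerns who enters. None of these acts on how the outcome is measured at 6 months.

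**Illustration of sensitivity under the Stage 1 rule**

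Inputs:
- Stage 1 minimum size n = 24 (Study Summary). Section 8.1 can be read as 24 + 6 = 30.
- Acceptance if the posterior probability of improvement exceeds 50% (8.2, Final decisions).
- Historical arm size m is not in the protocol; assumed 100 to 300.
- Net bias b is not known; assumed 0.1 or 0.2 SD.
- Normal outcome with SD 1, flat prior, no borrowing.

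Formulas: SE = sqrt(1/n + 1/m). With no true difference, P(accept) = Phi(b/SE).

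For n = 24:
- m = 100: SE = sqrt(0.0417 + 0.0100) = 0.227. With b = 0.1, Phi(0.1/0.227) = 0.670. With b = 0.2, 0.811.
- m = 300: SE = sqrt(0.0417 + 0.0033) = 0.212. With b = 0.1, Phi(0.1/0.212) = 0.681. With b = 0.2, 0.827.
- b = 0 gives 0.500 whatever m is.

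For n = 30, b = 0.1 gives 0.685 to 0.699 and b = 0.2 gives 0.832 to 0.852 over the same range of m.

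If the optimised programme were truly 0.2 SD worse, then at n = 24 acceptance would be 17-19% without bias and 50% with an offsetting bias of 0.2 SD.

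**The case against.** The strongest case against runs as follows.

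- **A reader might infer that the therapist reads the answers.** The protocol does not say so. It says that the therapist writes the walk distance in the form and scans it. What patients are told about confidentiality would be in information sheets not available here. What stands is that the therapist handles the form and can see it.
- **A reader might infer that the deliverer always runs the 6-month walk test.** Section 6.1 uses the same unspecific term for the baseline and repeat tests, and section 7.2 shows that the baseline assessor can be someone else. A repeat by the same assessor fits the wording equally well. What stands is that the assessor is not fixed.
- **A reader might infer that the bias is certain, favourable and wholly additive.** If the original trial collected outcomes in a similar way, some or all of it would cancel against that trial's BOOST arm. The protocol is silent, so the net size, and even the sign, is unknown. This objection stands. It is also a reason to state the comparison, since the design relies on it.
- **The illustration is not the plan's model.** Section 8.2 specifies commensurate and power priors, hierarchical models and baseline adjustment, and a single ODI item is not normal. This stands. A prior that shrinks symmetrically towards no difference would not change the sign of the estimate, so that kind of borrowing would not remove the effect at a 50% bar. The protocol does not fix the prior, however. The 50% starting point comes from the bar itself, not from outcome handling.
- **There are mitigations.** The accelerometer is posted to the patient, shows the patient no data, is processed by a separate team and enters the same models. It is a useful check that does not pass through the therapist, but it is not a primary outcome. Section 8.2 also calls the evidence not definitive and triangulates it with interviews, but those are with the therapists who deliver the programme.
- **Clinic staff collecting outcomes is a normal pragmatic choice in an implementation cohort.** That is fair, and no section is contradicted. The choice can still be improved at little cost.

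**Conclusion.** The point holds in a limited form. The protocol puts the completed self-report form in the hands of the delivering therapist, leaves the 6-month walk-test assessor open, and uses adjustments that cannot correct a difference in measurement at follow-up. Both primary outcomes are exposed. The satisfaction items are exposed too, but they are not primary.

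The protocol does not establish how large the bias is, or that any survives the comparison with the original trial. The 67-68% figure shows only how sensitive a 50% bar is to an assumed net bias of 0.1 SD, with 24 patients, an assumed historical arm of 100 to 300, a flat prior and no borrowing. It should not be read as the plan's error rate. Stage 2 has a different benchmark (not significantly worse than the original trial). Favourable bias would make that easier to meet as well, by an amount not calculated here.

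This is an inexpensive improvement that should be made, not a flaw that invalidates the study.

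**What to change.** In sections 6.1 and 9.6.2:

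1. The patient completes the 6-month self-report form at the visit and seals it in a pre-paid envelope that goes straight to the study team. This is the return route already used for patients who miss the visit. Patients are told that the therapist will not see the answers.
2. The 6-minute walk test is recorded on a separate sheet, which the site scans and emails as now.
3. Where a site already has a research physiotherapist who did the baseline test, that person repeats it at 6 months.
4. The protocol states how outcomes were assessed in the original trial and how the present procedure compares.

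Cost: protocol wording, one form split in two, and one pre-paid envelope per patient. No extra visit or staff is needed. The downsides are a slightly slower return than a scan and the loss of any chance to check missing items in clinic, which matters in a cohort this small. Where a site has no research physiotherapist, some encouragement bias in the walk test remains and should be reported as a limitation.
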